#### 6.4 Follow-up visit

30 days after end of treatment ( $\pm 10$  days) patients return for a follow-up visit. At this visit, blood pressure is measured (as described above); data on smoking, alcohol use, concomitant medication and AEs/SAEs are collected. A blood sample is taken only if there has previous blood parameters at earlier visits required follow-up. If trial medication was left at the patients home after the end of treatment visit, the remaining tablets will be collected, the number documented and the blisters will be sent back for disposal. The status of uploaded images will be double-checked; missing images will be retrieved and also uploaded. The investigator will continue to follow-up on all patients (also withdrawals) with AEs/ SAEs until the findings have been clarified or became stable. The follow-up visit may be waived if there was no unresolved SAE at time point end of treatment visit.

#### 6.5 Planned treatment after study end

After the subject has ended participation in the trial, the primary responsible physician (either a neurosurgeon, neurologist, or neuroradiologist) at the treating hospital will continue with standard care. The IMP does not need to be tapered off. The general physician will be responsible for blood pressure management after study end.

## 7 METHODS OF DATA COLLECTION

Please refer to the CLINICAL TRIAL SCHEDULE for parameters and time points captured.

## 7.1 Safety Parameters

### Adverse Events:

For definition see 8.1.1.

Adverse events will be interrogated for at each contact between the responsible investigator and the study subject. Furthermore, all pathological and clinically relevant findings in physical examinations, blood pressure, clinical chemistry, hematology, and clotting will be documented as adverse events.

Wherever possible, adverse events will be reported on the basis of CTCAE v5.

Adverse events will be reported with subject ID, start and end date, description, grading, seriousness, relationship, action taken and outcome.

### Blood pressure:

Systolic and diastolic blood pressure determined on all study days will be documented as numerical values on appropriate CRF-pages.

### 12-lead ECG

12-lead ECG may be recorded at any time at discretion of the responsible investigator, but only if medically imperative for clarification of clinical signs and symptoms. Pathological and clinically relevant findings will be documented as adverse events/ serious adverse events.

### Clinical chemistry, hematology and clotting:

Following parameters will be determined on the predefined study days:

Clinical chemistry: We will collect data on GFR and blood sodium in patients with pre-existing, compensated chronic renal failure (stage III), who are monitored for these parameters by their treating physicians.

After collection, the samples will immediately be delivered to the laboratory of the participating institution for respective determinations. All parameters will be documented on appropriate CRF-pages.

Further laboratory parameters may be determined at any time during the study at discretion of the responsible investigator. Pathological and clinically relevant findings will be documented as adverse events/ serious adverse events.

## 7.2 Efficacy Parameters

### Primary efficacy endpoint:

- Aneurysm rupture (i.e. aneurysmal subarachnoid hemorrhage, SAH) or growth (increase in any aneurysm diameter by  $\geq 1\text{mm}$ ) on serial imaging (either two MR or CT angiographies) within 36 +/- 6 months from randomization.

### Secondary efficacy endpoints:

1. Any growth or rupture of aneurysm during follow-up irrespective of the duration of trial participation
2. Difference of aneurysm volume (defined as increase of aneurysm volume in computerized measurements from source images by  $>10\%$  and  $>3\text{mm}^3$ ) or aneurysm shape (e.g. development of daughter sac)
3. Development of de novo aneurysm on serial imaging

4. If a second aneurysm is present: Growth in diameter or volume and alteration of shape of this second aneurysm.
5. Clipping/coiling during the study period
6. Any ischemic or haemorrhagic stroke, defined as clinical symptoms of stroke AND a compatible lesion on imaging
7. Myocardial infarction defined as increase of Troponin, CKMB and/or presence of new significant Q waves obtained in ECG
8. Vascular death (including fatal stroke, fatal myocardial infarction, sudden death)
9. Death from all other causes
10. Major spontaneous bleeding requiring hospitalisation defined as substantially disabling bleeding, intraocular bleeding leading to the loss of vision, or bleeding necessitating the transfusion of at least 2 units of erythrocyte concentrates
11. Blood pressure; any data on blood pressure management used
12. Safety aspects (adverse and serious adverse events, including those mentioned above, see also 8.1.6 and 8.2)
13. Quality of life, as determined by completion of the paper-based EQ-5D-5L form by patient.

#### 7.2.1 Progression-free Survival

Progression-free survival, defined as the time from randomization to the first observation of aneurysm growth or rupture, will be assessed every 12 months, based on available data such as subsequent imaging, until study end. During the course of the study, timing of subsequent imaging of the intracranial aneurysm will be at the discretion of the treating physician, since there are currently no guidelines in this respect. However, we anticipate that many centers will perform imaging every one or two years. If a patient is lost to follow up, progression-free survival is censored at the time of last imaging. No x-ray or other radiation is used for trial purposes only. However, if the patient undergoes examinations for medical reasons (such as routine control of aneurysm) such examinations may be used for a second assessment for trial purposes.

#### 7.2.2 Overall Survival

Survival data will be collected continuously during the study period (treatment phase) until study end. If a patient is lost to follow up, overall survival time is censored at the time of last contact.

## 8 ADVERSE EVENTS

### 8.1 Definitions

#### 8.1.1 Adverse Event

According to GCP, an adverse event (AE) is defined as follows: Any untoward medical occurrence in a subject administered a pharmaceutical product and which does not necessarily have a causal relationship with this treatment. An AE can therefore be any unfavourable and unintended sign (including an abnormal laboratory finding), symptom, or disease temporally associated with the use of a medicinal (investigational) product, whether or not related to the medicinal (investigational) product.

An AE may be:

- New symptoms/ medical conditions
- New diagnosis
- Changes of laboratory parameters

The criteria that should be considered when determining whether an abnormal test finding should be reported as adverse event are as follows:

- Test result is associated with accompanying symptoms, and/or
  - Test result require diagnostic testing or medical/surgical intervention, and/or
  - Test result lead to a change in trial dosing outside the protocol-stipulated dose adjustments, or discontinuation from the trial, significant additional concomitant drug treatment, or other therapy, and/or
  - Test result is considered clinically relevant at the discretion of the investigator or sponsor
- Intercurrent diseases and accidents
  - Worsening of medical conditions/ diseases existing before clinical trial start
  - Recurrence of disease
  - Increase of frequency or intensity of episodic diseases.

A pre-existing disease or symptom will not be considered an adverse event unless there will be an untoward change in its intensity, frequency or quality. This change will be documented by an investigator.

Surgical procedures themselves, including aneurysm surgery, are not AEs; they are therapeutic measures for conditions that require surgery. The condition for which the surgery is required may be an AE. Planned surgical measures permitted by the clinical trial protocol and the condition(s) leading to these measures are not AEs, if the condition leading to the measure was present prior to inclusion into the trial. In the latter case the condition should be reported as medical history.

AEs are classified as "non-serious" or "serious".

### 8.1.2 Serious Adverse Event

A serious adverse event (SAE) is one that at any dose:

- Results in death
- Is life-threatening (the term life-threatening refers to an event in which the subject was at risk of death at the time of event and not to an event which hypothetically might have caused death if it was more severe)
- Requires hospitalisation or prolongation of existing hospitalisation\*
- Results in persistent or significant disability/ incapacity\*\*
- Is a congenital anomaly/ birth defect or
- Is otherwise medically relevant

\* Hospitalisation for performing *preventive* aneurysm treatment is not classified as an SAE. Hospitalisations for disease-related procedures (surgery, imaging, laboratory tests) or any procedures planned before entry into the study are not considered SAEs. Hospitalisations for social reasons in the absence of an adverse event are not classified as SAEs either.

\*\* Persistent or significant disability or incapacity means that there is a substantial disruption of a person's ability to carry out normal life functions. The irreversible injury of an organ function (e.g. paresis, diabetes, cardiac arrhythmia) fulfils this criterion.

Medical and scientific judgement will be exercised in deciding whether expedited reporting is appropriate in other situations - such as important medical events that may not be immediately

life threatening or result in death or hospitalisation but may jeopardise the patient or may require intervention to prevent one of the other outcomes listed above. These should also usually be considered serious (examples of such events are intensive treatment in an emergency room or at home for allergic bronchospasm; blood dyscrasias or convulsions that do not result in hospitalisation; or development of drug dependency or drug abuse).

SAE reporting will be coordinated by the KKS pharmacovigilance.

#### 8.1.3 Serious Adverse Reaction

SAEs that potentially may be attributed to the investigational medicinal product (IMP) are classified as Serious Adverse Reactions (SARs).

#### 8.1.4 Expectedness

An 'unexpected' adverse reaction is an adverse reaction of which the nature or severity is not consistent with the applicable product information, (Summary of Product Characteristics, SmPC). Furthermore, reports which add significant information on specificity or severity of a known adverse reaction constitute 'unexpected' events.

#### 8.1.5 Suspected Unexpected Serious Adverse Reaction (SUSAR)

SAEs that are both 'suspected', i.e., possibly related to the study drug (investigational medicinal product (IMP)) and 'unexpected', i.e., the nature and/ or severity of which is not consistent with the applicable product information are to be classified as Suspected Unexpected Serious Adverse Reactions (SUSARs).

In case, either the investigator who primary reported the SAE or the second assessor, classifies the SAE as 'suspected' (*i.e., either as 'definitely' or 'probable' or 'possible' related to IMP or 'not assessable'*) and the SAE is unexpected it will be categorised as a SUSAR.

All SUSARs are subject to an expedited reporting to the responsible ethics committee(s), the competent authorities and to all participating investigators.

### Grading of AEs

The grading of AEs in this trial will be carried out on the basis of the 5-grade scale defined in the CTCAE v5.0:

- Grade 1: Mild: signs and symptoms that can be easily tolerated. Symptoms can be ignored or disappear when the subject is distracted.
- Grade 2: Moderate: symptoms cause discomfort but are tolerable, they cannot be ignored and affect normal activity.
- Grade 3: Severe: symptoms strongly affect normal activity.
- Grade 4: Life threatening or causing disablement
- Grade 5: Death

The grading of all AEs listed in the CTCAE v5.0 will be based on the information contained therein. The grading of all other AEs, i.e., those which are not listed in the CTCAE v5.0 will be performed by a responsible investigator, based on definitions given above.

Clarification of the difference in meaning between "serious" and "severe":

The terms "serious" and "severe" are not synonymous. The term 'severe' should be used to describe the intensity (severity) of a specific event; the event itself, however, may be of relatively minor significance (such as severe headache). This is not the same as "serious", which is based on the existence of one of the above mentioned seriousness criteria.

#### 8.1.6 Relationship and Outcome of AEs

The investigator will evaluate each AE that occurred after randomisation. Regarding the **relationship** with the administration of the IMP it will be assessed:

- Definitely related:** There is a reasonable possibility that the event may have been caused by the IMP. A certain event has a **strong temporal relationship** and an alternative cause is unlikely.
- Probable:** An AE that has a reasonable possibility that the event is likely to have been caused by the IMP. The AE has a **timely relationship** and **follows a known pattern of response**, but a potential alternative cause may be present.
- Possible:** An AE that has a reasonable possibility that the event may have been caused by the IMP. The AE has a **timely relationship** to the IMP; **however, the pattern of response is untypical**, and an alternative cause seems more likely, or there is significant uncertainty about the cause of the event.
- Unlikely:** Only a remote connection exists between the IMP and the reported adverse event. Other conditions including concurrent illness, progression or expression of the disease state or reaction of the concomitant medication appear to explain the reported adverse event.
- Not related:** An AE that does not follow a reasonable temporal sequence related to the IMP and is likely to have been produced by the subject's clinical state, other modes of therapy or other known aetiology.
- Not assessable:** There is insufficient or incomplete evidence to make a clinical judgement of the causal relationship.

All subjects who have reportable AEs, whether considered associated with the use of the trial medication or not, must be monitored to determine the **outcome**. The clinical course of the AE will be followed up until resolution or normalisation of changed laboratory parameters or until it has changed to a stable condition. This also holds for on-going AEs/SAEs of withdrawn subjects.

The outcome of an AE at the time of the last observation will be classified as:

- Recovered / resolved:** All signs and symptoms of an AE disappeared without any sequels at the time of the last interrogation.
- Recovering / resolving:** The intensity of signs and symptoms has been diminishing and / or their clinical pattern has been changing up to the time of the last interrogation in a way typical for its resolution.
- Not recovered/not resolved:** Signs and symptoms of an AE are mostly unchanged or worsened at the time of the last interrogation.

|                                   |   |
|-----------------------------------|---|
| Recovered / resolved with sequel: | Actual signs and symptoms of an AE disappeared but there are sequels related to the AE.   |
| Fatal:                            | Resulting in death. If there is more than one adverse event, only the adverse event leading to death (possibly related) will be characterised as 'fatal'. |
| Unknown                           | The outcome is unknown or implausible and the information cannot be supplemented or verified.   |

The action taken with the IMP will be assigned to one of the following categories:

|                   |   |
|-------------------|---|
| Dose not changed: | No change in the dose of the IMP.   |
| Dose reduced:     | Reduction in the dose of the IMP.   |
| Dose increased:   | Increase in the dose of the IMP.  |
| Drug withdrawn:   | Discontinuation (temporary or permanent) of the IMP.                                |
| Unknown:          | The information is unknown or implausible and it cannot be supplemented or verified |
| Not applicable:   | The question is implausible (e.g. the subject is dead).                             |

The term "countermeasures" refers to the specific actions taken to treat or alleviate adverse events or to avoid their sequels. Following categories will be used to categorise the countermeasures to adverse events:

|                 |  |
|-----------------|--|
| None:           | No action taken.   |
| Drug treatment: | Newly-prescribed medication or change in dose of a medication. |
| Others:         | Other countermeasures, e.g. an operative procedure.            |

## 8.2 Period of Observation and Documentation

Adverse events (AEs) will be ascertained by the investigators using non-leading questions, noted as spontaneously reported by the patients to the medical staff or observed during any measurements on all study days. The observation period begins with the randomisation and ends with the last study visit, 30 days +/-10 days after end of treatment visit (or after withdrawal) (i.e. follow-up-visit). AEs will be documented in the patient file and in the CRF. All subjects who present AEs, whether considered associated with the use of the trial medication or not, will be monitored by the responsible investigator to determine their outcome; this applies to withdrawals too (see also 8.1.7).

The end date of the SAE is defined typically the same as for AEs. The end date of the SAE must not be later than the end date of the corresponding AE.

AEs and SAEs that are on-going at the time of death are considered not resolved or resolving.

The patients should report any AEs occurring during the outpatient part to the study centre by phone.

|   |   |                               |
|---|---|-------------------------------|
| Clinical Trial Code: Protect-U
EudraCT: 2017-000514-35 | Trial Protocol
Version 07 - August 23 - 2022 | Page 44 of 62
CONFIDENTIAL |
|---|---|-------------------------------|

All SAEs and their relevance for the benefit/risk assessment of the study will be evaluated continuously during the study and for the final report. All SAEs will be documented in the "Serious Adverse Event" form (see 8.3).

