## CLINICAL TRIAL SCHEDULE

| Visit No.                                    | Visit 0                      | Visit 1        | Visit 2              | Visit 3 - 20               | Visit 21                                      | Visit 22  |
|--|------------------------------|----------------|----------------------|----------------------------|---|---|
|  | Screening*                   | Baseline       | Treatment phase      |                            | End of treatment/
study                    | Follow-up   |
| Day  | 0 – 30 days prior to visit 1 | Day 0          | 6 months +/- 30 days | every 6 months +/- 30 days | Month 36 +/- 30 days or month 120 +/- 30 days | 30 +/- 10 days after end of treatment visit (or after withdrawal) |
| Procedure                                    |                              |                |                      |                            |   |   |
| Written informed consent                     | ● (S)**                      |                |                      |                            |   |   |
| Inclusion/ exclusion criteria                | ● (S)                        | ●              |                      |                            |   |   |
| Demographic data, vital signs                | ●                            |                |                      |                            |   |   |
| Medical history                              | ● (R)**                      |                |                      |                            |   |   |
| Smoking status and alcohol consumption       | ●                            | ●              | ●                    | ●                          | ●   | ●   |
| Randomization                                |                              | ●              |                      |                            |   |   |
| Pregnancy test                               | ●  (S)           | ●  |                      |                            |   |   |
| Concomitant medication                       | ● (R)                        | ●              | ●                    | ●                          | ●   | ●   |
| AE   |                              | ●              | ●                    | ●                          | ●   | ●   |
| Aneurysm/ baseline characteristics           |                              | ●              |                      |                            |   |   |

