| IMP accountability 1/5            |                              | ●              | ●                    | ●                          | ●   |   |
| Blood pressure (bp), seated                  |                              | ●              | ●                    | ●                          | ●   | ●   |
| Supply with bp device            |                              | ●              |                      |                            |   |   |
| Clinical chemistry               | ●                            | ●              | ●                    | ●                          | ●   | ●   |
| Cardiovascular outcome                       |                              |                | ●                    | ●                          | ●   | ●   |
| EQ-5D-5L                                     |                              | ●              | ●                    | ●                          | ●   | ●   |
| Check for imaging***/
upload if available |                              | ●              |                      | ● (at least once a year)   | ●   | ●   |

\*# Screening and baseline visit may be combined at just one visit, if verification of all inclusion and exclusion can be ensured at this visit, and the patient has ample time to consider participation.

\*\* (S) = study specific / (R) = Clinical routine

\*\*\* Either CTA or MRA as per standard of care (SOC), if new imaging is available

1 application of trial medication by patient at home once daily from day 0 to end of treatment; patients of intervention group only

2 applicable for females of childbearing potential only. Test must be repeated on Day 0 if result of initial test is not valid on Day 0 (depending on period/ menstrual cycle)

3 data on GFR and blood sodium in patients with pre-existing, compensated chronic renal failure, or other parameter such as INR, thrombocytes count, haemoglobin, if needed to confirm inclusion/exclusion criteria and/or if perceived necessary by investigator.

Data not older than 6 months from certified labs may be used.

4 applicable only if any SAEs have not been resolved at previous visits

5 applicable only for patients of intervention group

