## **3.2 Trial Duration and Schedule**

The duration of the trial for each subject is expected to be at least 36 months intervention and one-month follow-up. For those subjects enrolled early in the trial, the intervention will be continued until the last subject enrolled completed the 36 months of intervention (maximum duration of treatment 120 months ± 30 days).

The overall duration of the trial is expected to be approximately 162 months. Recruitment of subjects has been started in in Q3 2017 in Germany. The actual overall or recruitment duration may vary. Based on a planned interim analysis, the DSMB can recommend modifying the duration of the trial. The study end is defined as "last patient out" (LPO), this may apply as well to a follow-up visit, if appropriate.

|  |                    |
|--|--------------------|
| Duration of the clinical phase for each patient: | [up to 120 months] |
| Total trial duration:                            | [162 months]       |
| Duration of clinical phase:                      | [144 months]       |
| Beginning of the preparation phase:              | [Q2 2017]          |
| FSI (first subject in):                          | [Q3 2017]          |
| LSI (last subject in):                           | [Q2 2026]          |
| LSO (last subject out):                          | [Q2 2029]          |
| DBL (database lock):                             | [Q3 2029]          |
| Statistical analyses completed:                  | [Q4 2029]          |
| Trial report completed:                          | [Q2 2030]          |

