- Existing or intended pregnancy, lactation in patients of the intervention group. If patients in the control group become subsequently pregnant and/or need to breastfeed after randomisation, they will not be excluded from the trial.

All patients who finish the study prematurely will be asked to attend a follow-up visit and to return unused trial medication. The patient must be asked to consent to this last examination. The withdrawal examination will be documented in the CRF.

If a patient does not come to a visit, the patient will be contacted and asked for information. If the patient wants to withdraw and agrees to give explaining reasons, the reason should be documented in the patients file and in the CRF.

In case of early withdrawal, the last aneurysm imaging will be used for the primary outcome analysis (*last observation carried forward*).

If a patient has severe side effects from one component of the intervention only, (e.g. severe orthostatic hypotension from intensive blood pressure control or major gastrointestinal bleeding from ASA), it can be decided to adjust or stop the component of the intervention causing the side effects, while continuing the other component of the intervention.

For documentation of AEs and SAEs see 8.1.6 and 8.2.

| Term                         | Definition   | Comment/ Sample  |
|------------------------------|--|--|
| Drop-out, study              | 
Participation terminated completely, including follow-up
 
Possible reasons:
 
 
• Patient withdraws consent: Withdrawal
 
• Patient moved/cannot be contacted
 
• Interventions cannot be performed due to medical reasons
 
• Non-compliance of patient
 
 
Drop-out after completion of study intervention:
Lost to follow-up
 
Final examination will be performed, if patient agrees. Study-Completion/ Withdrawal-form will be completed.
 | 
ITT-sample
 
ITT-sample (if study intervention completed)
  |
| Drop-out, study intervention | Termination of study intervention, follow-up once as per protocol.   | ITT  |
| Screening-failure            | 
Exclusion criteria given prior to screening / enrolment:
 
Patient will be recorded at screening list, but will not be provided with a patient number.
   | -  |

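### Adverse-event observation is set to run to a visit about 30 days after treatment for every patient, but that visit is conditional, so post-treatment questioning depends on earlier harm or withdrawal

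*Protocol*

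**What the plan says.** Two sections give every patient a post-treatment observation period.

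- Section 8.2 states: "The observation period begins with the randomisation and ends with the last study visit, 30 days +/-10 days after end of treatment visit". It extends the same window to withdrawn patients and makes no exception for anyone.
- Section 3.2 states: "The duration of the trial for each subject is expected to be at least 36 months intervention and one-month follow-up".

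The Clinical Trial Schedule agrees on timing. It places Visit 22 about 30 days after end of treatment or withdrawal and marks AE and cardiovascular outcome collection there.

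Three other places decide who actually has that visit.

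- Schedule footnote 4, attached to the Visit 22 column: "applicable only if any SAEs have not been resolved at previous visits".
- Section 6.4 opens by saying that "patients return for a follow-up visit" and closes with: "The follow-up visit may be waived if there was no unresolved SAE at time point end of treatment visit".
- Section 4.6.1, on withdrawals: "All patients who finish the study prematurely will be asked to attend a follow-up visit". SAE status is not mentioned.

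Section 8.2 also tells patients to telephone the centre if an AE occurs. No scheduled contact is named to replace a visit that is not held.

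**The concern.** The protocol defines a window in which AEs count as observed, then makes the visit that closes it depend on what has already happened to the patient. A completer with no open SAE may have no scheduled contact after the end-of-treatment visit. A completer with an open SAE, or a patient who withdrew, is seen again and questioned.

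Both conditions arise after randomisation, and both can differ by arm. Some withdrawal reasons in section 4.6.1 can arise only in the intervention arm: lack of efficacy of the experimental intervention, and intolerable events from both of its components. Pregnancy is a withdrawal reason there, while controls who become pregnant stay in. Treatment is open-label, so questioning in this month could be unequal between arms for reasons other than the true event rate.

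The month also matters in its own right. Under sections 6.3 and 6.5 the trial drug is stopped unless there is an indication to continue, and blood-pressure care passes to the general practitioner. Stroke, myocardial infarction, death, major bleeding and AEs are secondary endpoints in section 2.2.

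**Working it through.** The protocol states no figure to reproduce here. The check sets the passages side by side and then bounds the size.

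**Who is questioned in the post-treatment month**

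| Patient | Sections 3.2 and 8.2 | Footnote 4 | Sections 6.4 and 4.6.1 |
|---|---|---|---|
| Completer, unresolved SAE | observed to the visit | visit applies | visit applies |
| Completer, no unresolved SAE | observed to the visit | visit does not apply | visit is the default but may be waived (6.4) |
| Withdrawn, unresolved SAE | observed to the visit | visit applies | asked to attend (4.6.1) |
| Withdrawn, no unresolved SAE | observed to the visit | visit does not apply | asked to attend (4.6.1) |

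This gives three results.

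1. In the second and fourth rows the texts cannot all be followed. Footnote 4 excludes the visit. For completers section 6.4 only makes it optional, and for withdrawals section 4.6.1 asks for it.
2. Where the visit is not held, section 8.2 has no event that ends AE observation.
3. Sections 6.4 and 8.1.6 require open AEs, including non-serious ones, to be followed until resolved or stable. An open non-serious AE nevertheless does not trigger the visit.

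**Size**

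Inputs: at least 36 months of treatment (section 3.2); visits every 6 months on a schedule that does not differ by arm (section 6.3); one nominal month after treatment; and *p*, the proportion of an arm that has the visit. The protocol gives no value for *p*.

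Scheduled observation per completer, in months: T = 36 + 1 × *p*.

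- Assumed for illustration, *p* = 8% against 4%: 36.08 / 36.04 = 1.0011, a difference of 0.11%.
- Extreme case, all of one arm and none of the other, at 36 months: 37 / 36 = 1.028, or 2.8%.
- The same extreme at the 120-month maximum: 121 / 120 = 1.008, or 0.8%.

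If the event rate is constant over time, these are also the relative differences in expected recorded events. If the rate changes after treatment stops, the excess scales with the rate in that month, for which the protocol gives no figure. The calculation concerns completers. A patient withdrawn early has a shorter base, so the extra month is a larger share for that patient.

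**The case against.** The strongest reply is that the consequence is slight. Every completer has at least 36 months of AE collection on the same six-monthly schedule in both arms, so unequal questioning in one further month moves total observation very little. That stands.

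Other parts of the reply also stand. Attendance is the default in section 6.4, and only footnote 4 makes the visit exclusive. Patients are asked to telephone about AEs, SAEs are reportable within 24 hours of becoming known (8.3), any subarachnoid haemorrhage is monitored and notified (9.4), and known AEs must be followed up. What is lost is systematic questioning, not all capture. A reader might infer that strokes, ruptures or SAEs in that month go unrecorded, or that nearly all completers have no contact. The documents support neither. They leave several reporting routes open and give no rate of unresolved SAEs from which to work out a share.

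It can also be said that the visit was always meant to be conditional, since section 3.2 lets study end fall at a follow-up visit if appropriate, and that the analysis window belongs in the statistical analysis plan, which is not shown. The first point explains the waiver as a deliberate reduction of burden, but section 8.2 was not brought into line with it. The second is fair for the analysis window. It does not answer the collection question, because no analysis plan can recover events that nobody asked about.

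**Conclusion.** The contradiction holds on the text alone. Sections 3.2 and 8.2 promise every patient a post-treatment AE window. Footnote 4 and section 6.4 make the visit that closes it conditional, and in different ways. Section 4.6.1 adds a third rule for withdrawals. Scheduled questioning in that month is therefore conditional on earlier harm or withdrawal, and the end of AE observation is undefined for patients without the visit.

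The effect is small. For completers it is about 0.1% of scheduled observation time under the assumed 8% against 4%, and at most 2.8% at a nominal month after 36, given a constant event rate. The primary endpoint is largely untouched. A reader might conclude that the between-arm safety comparison is materially biased, or that unobserved days will be counted as observed. Neither follows: the magnitude is slight, any imbalance between arms is possible rather than shown, and the protocol fixes no between-arm AE analysis window. This is a cheap improvement worth making, not a threat to the trial's conclusions.

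**What to change.** Reconcile footnote 4 of the Clinical Trial Schedule with sections 3.2, 4.6.1, 6.4 and 8.2, so that one AE window applies to all patients in both arms and its end is defined when the follow-up visit is not held. Either of two forms would do.

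- **Close at a common point.** End the between-arm AE comparison at the end-of-treatment or withdrawal visit for everyone, and list later events separately. This is a wording change. The cost is that post-treatment events leave the formal comparison.
- **Contact everyone.** Whenever the visit is not held, make a telephone contact in both arms at 30 days, asking about AEs, SAEs, hospital admissions and new imaging. The cost is one short call per patient. Section 6.3 already accepts telephone visits, for controls after an on-site visit and for all patients if the pandemic cancels visits.

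With last subject out planned for Q2 2029, patients who reach end of treatment after the amendment would be covered.
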